### 8.8.2 Serious Adverse Events

A serious adverse event (SAE) is any untoward medical occurrence that meets one or more of the following criteria:

- Led to death
- Led to a serious deterioration in the health of the subject that:
  - Resulted in a life-threatening illness or injury
  - Resulted in a permanent impairment of a body structure or body function
  - Required in-patient hospitalization or prolongation of existing hospitalization
  - Resulted in medical or surgical intervention to prevent permanent impairment to body structure or body function
- Led to fetal distress, fetal death, or congenital abnormality or birth defect.

### 8.8.3 Anticipated Adverse Events/Device Related Adverse Events

A variety of complications are expected to occur in subjects undergoing CPB and cardiac surgery, regardless of whether or not CytoSorb is used. These may include, but are not limited to:

Serious, but less common, risks:

- Bleeding during or after the surgery including bleeding in relation to anticoagulation
- Blood clots that can cause heart attack, stroke, or lung problems
- Heparin-induced thrombocytopenia
- Bypass induced thrombocytopenia
- Reduction in platelets
- Infection, including pneumonia
- Organ injury including:
  - Respiratory damage causing breathing problems or failure to wean from the ventilator
  - Cardiac dysrhythmias/arrhythmias
  - Kidney injury
  - Cognitive impairment
- Death

Less serious, but more common risks and adverse events:

- Low-blood pressure
- Nausea and/or vomiting
- Chills
- Allergic response to device materials
- Reduction in platelet count
- Reduction in white blood cell count
- Reduction in proteins (albumin, total protein)
- Coagulation within device
- Heparin-induced thrombocytopenia

Potential Adverse Device Events Related to CytoSorb:

- Removal of drugs and hormones
- Allergic response to device materials
- Reduction in platelet count
- Reduction in white blood cell count
- Reduction in proteins (albumin, total protein) which may increase with CPB duration.
- Reductions in albumin may result in a reduction in serum calcium

- Coagulation within device
- Infection
- Blood loss
- Hypothermia and chills
- Hemolysis
- Device leakage
- Circuit leakage
- Death

## 8.8.4 Unanticipated Adverse Device Effect

An unanticipated adverse device effect (UADE) is any serious adverse effect on health or safety or any life-threatening problem or death caused by, or associated with the device, if that effect, problem, or death was not previously identified in nature, severity, or degree of incidence in the investigational plan or application (including a supplementary plan or application), or any other unanticipated serious problem associated with a device that relates to the rights, safety, or welfare of subjects.

## 8.8.5 Device Malfunction/Observations

If there is a device malfunction or other observation with the CytoSorb device, the Investigator (or designee) is required to complete the Device Observation eCRF to notify the Sponsor immediately and indicate if the observation resulted in an adverse event and indicate if complications are related to the device, procedure or underlying disease.

In the event of a suspected observation or device problem, the device shall be returned to the Sponsor for analysis. Instructions for returning the investigational device are included in the Study Reference Manual.

If the Investigator cannot determine the cause of the event, it should be classified as unknown.

## 8.9 **Reporting Procedures**

## 8.9.1 Investigator Reporting

The Investigator at each participating center is ultimately responsible for reporting adverse events to the Sponsor or its designee. The information to be reported on the adverse event should include the start date of the adverse event, treatment, resolution, and assessment of both the seriousness and the relationship to the investigational device. The Investigator (or designee) is required to complete the adverse event eCRF at each study visit if an adverse event occurs. One adverse event eCRF must be completed for each adverse event. Investigators must report SAEs/UADEs to the Sponsor within 24 hours of investigational site knowledge of event

occurrence by entering data into the eCRF. The Investigator should report all serious adverse events to the IRB as required.

If there is a device malfunction or other observation, the Device Observation CRF requires the Investigator to notify the Sponsor within 24 hours, indicate if the observation resulted in an adverse event and indicate if complications are related to the device, procedure or underlying disease.

In the event of a suspected observation or device problem, the device shall be returned to the Sponsor for analysis. Instructions for returning the investigational device are included in the Study Reference Manual.

### 8.9.2 Sponsor Reporting

All adverse events will be reported to the regulatory authority/FDA at least annually.

### 9. STUDY OVERSIGHT

### 9.1 Clinical Events Committee

An independent group of physicians that are not involved in the clinical investigations will act as the Clinical Events Committee (CEC) under the direction of the CRO. The CEC will be responsible for the review and validation of reported potential ENDPOINT adverse events (i.e. all device/procedure related SAEs) that occur within 30 days post procedure per the CEC Charter. Policies and procedures governing the work of the CEC will be provided in a CEC Charter. The CEC Charter will be developed prior to the start of study enrollment.

### 9.2 Data Monitoring Committee (DMC)

The study will utilize a Data Monitoring Committee (DMC) which will be comprised of three (3) total members (2 physicians and a biostatistician) with relevant clinical/medical experience with the product and/or indication/disease under clinical investigation. The primary role of the DMC is to oversee the safety of subjects enrolled into the study. The membership of the committee will be independent from the investigative sites and study sponsor in order to reduce any potential for perception of bias and to remain free from potential conflicts of interest. In order to oversee the safety of subjects as they are enrolled into the study, the DMC will establish a charter including a mission statement, operating procedures, and proposed monitoring criteria for the study, including any required interim analysis time points for assessing safety and proposed study stopping rules, if appropriate. The DMC will meet to ratify their operational charter within a reasonable timeframe relative to the enrollment of the first few subjects entering into the study. Written recommendations from the DMC will be provided to the study sponsor.

### 9.3 Central Laboratory

A central laboratory shall be utilized to analyze some of the blood samples, and some of the urine samples collected in this study. The sample size and shipping requirements are provided to the sites in the Study Laboratory Manual. All sites will be trained on the collection, preparation, and shipping requirements for central laboratory samples.

### **10. STUDY MONITORING**

The CRO will monitor and manage the data for the investigational study on behalf of the Sponsor, CytoSorbents, Inc. Some co-monitoring and remote data checking will also be done by Sponsor. A study specific monitoring plan will be created to ensure protocol compliance and applicable regulatory requirements.

Clinical monitors will verify subject data and ensure compliance is consistent with Good Clinical Practice (GCP), clinical protocol and other study requirements, according to the guidelines per the Monitoring Plan, set forth in CROs monitoring Standard Operating Procedures (SOPs), and 21 CRF Part 812.

### **10.1 Monitor Training**

The Sponsor and/or designated monitors will be trained appropriately to monitor study progress including but not limited to the protocol and eCRFs, and per the Monitoring Plan.

### 10.2 Site/Investigator Training

The Sponsor and CRO shall be jointly responsible for providing training to the Investigator and appropriate clinical site personnel on the following topics:

- Protocol
- EDC/Database operations
- Central Laboratory Requirements
- CytoSorb® Device

### 10.3 Site Monitoring

Completed eCRFs will be verified by the monitor both at the investigational sites and remotely at regular intervals throughout the study. The Investigator will allow the monitor and/or representative of the Sponsor, and any regulatory body to review and inspect the study files, subject eCRFs, subject medical records and other related study documents as required.

All eCRFs will be reviewed for completeness and clarity. Missing or unclear data will be investigated by the monitor and will be retrieved, clarified and entered by study personnel as necessary throughout the study. CytoSorbents, Inc., or their authorized representative may request additional documentation from the Investigator such as physician procedure notes or physician written summaries when adverse events are observed and reported.

### **10.4 Regulatory Agency Inspection**

In the event that an Investigator is contacted by a regulatory agency regarding this study, the Investigator will notify the Sponsor or its designee immediately. The Investigator and research coordinator must be available to respond to reasonable requests and queries made during the inspection process. The Investigator must provide the Sponsor or designee with copies of all correspondence that may affect the review of the current trial (e.g., Form FDA 483, Inspectional Observations and Warning Letters). The Sponsor may provide needed assistance in responding to regulatory audits.

### **11. STATISTICAL CONSIDERATIONS**

General statistical considerations: Descriptive statistics will be the mean, standard deviation, median, minimum and maximum for continuous variables and count and percent of patients for categorical variables. Statistical analyses will be carried out using SAS Version 9.4 or later and/or the R software language.

### **11.1 Analysis Populations**

Intent-to-Treat (ITT): All randomized patients.

Modified Intent-to-Treat (mITT): All randomized patients who meet all inclusion criteria through the completion of the surgical procedure. There are two mITT analysis sub-populations defined as follows:

- The primary sub-population includes all subjects enrolled and randomized to the treatment group who are undergoing valve replacement with another procedure (e.g., CABG, valve replacement) *without* Hypothermic Circulatory Arrest (HCA). This is the primary population for efficacy analyses.
- The secondary sub-population consists of all surgical subjects enrolled and randomized to the treatment group who are undergoing aortic reconstructions with or without other procedures (e.g., CABG, valve replacement) *with* HCA. This is a secondary population for efficacy analyses.

The primary analyses on the primary efficacy endpoint will be performed on these subpopulations. Subjects will be analyzed according to the treatment to which they were randomized.

Safety: Comprised of all roll-in and randomized subjects in whom treatment was attempted. Safety analysis will be performed on this population; it will also be performed separately on the above mITT populations. Patients will be summarized according to the actual treatment received.

Per Protocol (PP): Defined as the subset of patients in the mITT sub-population who had no major protocol violations. Efficacy analyses on the two PP sub-populations will be considered secondary. Patients will be analyzed by actual treatment received.

Roll in patients are not randomized and are only included in the safety population.

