### 6.3.2 Primary Effectiveness Endpoint(s)

The primary effectiveness endpoint is the incidence or severity of AKI in the first 48 hours after surgery when used intraoperatively with cardiopulmonary bypass (CPB) in subjects undergoing cardiac surgery as defined by the KDIGO clinical practice guideline through 48 hours post-cardiac surgery. Assessment of serum creatinine and hourly measurements of urine output will be recorded for the first 48 hours following admission to the ICU. The intended primary effectiveness sub-population includes all subjects enrolled and randomized to the treatment group who are undergoing valve replacement with another procedure (e.g., CABG, valve replacement) *without* Hypothermic Circulatory Arrest (HCA). Balance between patients undergoing cardiac surgery with and without HCA will be evaluated during the interim analysis and the primary sub-population confirmed.

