#### 6.4.1 Inclusion Criteria

1. Male or female and  $\geq 18$  years of age.

- 2. Schedule for non-emergent surgical procedures requiring CPB with full sternotomy:
  - a. Any combination of heart valve replacement or valve repair and another procedure (e.g., CABG) *without* HCA, coronary artery bypass graft (CABG) alone excluded OR
  - b. Aortic reconstruction alone *with* HCA OR
  - c. Aortic reconstruction with any combination of valve repair or valve replacement or CABG (but not CABG alone) *with* HCA
- 3. Estimated glomerular filtration rate (eGFR) ≥ 30 ml/min/1.73m^2 and at least ONE of the following additional risk factors for Cardiac Surgery Associated (CSA)-AKI:
  - a. Age  $\geq$  75 years
  - b. Previous cardiac surgery with sternotomy;
  - c. Documented New York Heart Association (NYHA) Class III or IV heart failure within 1 year prior to surgery;
  - d. Left ventricular ejection fraction (LVEF) ≤ 35% by invasive or noninvasive diagnostic cardiac imaging echocardiography, nuclear imaging, computed tomography, magnetic resonance imaging or angiography performed within 90 days prior to surgery. (If LVEF ≤ 35% by any invasive or noninvasive imaging procedure, patient meets the risk factor.)
  - e. Insulin-requiring diabetes;
  - f. Non-insulin-requiring diabetes AND the presence of  $\geq$  +2 proteinuria on urinalysis (medical history or dipstick);
  - g. Preoperative anemia (hemoglobin < 11g/dl)
  - h. BMI  $\ge$  30 kg/m^2

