### 11.1.2 Effectiveness evaluations:

The primary endpoint will be assessed in each modified intent-to-treat (mITT) population in step-wise fashion beginning with the primary sub-population. If a significant beneficial effect is met for CytoSorb over control at a one-sided overall 0.025 level of significance, then the study will be considered to be a primary endpoint statistical success on this subpopulation and testing will proceed to the secondary sub-population. Otherwise the study will be considered to have statistically failed the primary endpoint.

We have selected to use a modified intent-to-treat population (mITT) population to avoid the consequence of including patients that were excluded from the study after randomization due to administrative reasons.

Use of the mITT population as defined is not anticipated to result in bias or informative censoring of the data.

The primary endpoint (rank order presence and severity of AKI) will be compared between treatments with Wilcoxon Rank Sum test. Continuous endpoints will be assessed via ANCOVA with baseline value as covariate. Binary endpoints will be assessed via unconditional exact binomial test. The primary endpoint will be summarized by subgroup factors, e.g., those who receive IV contrast within 48 hours prior to surgery versus those who do not. Additionally, subgroup-by-treatment interaction may be tested via generalized ordered categorical model and/or for binary combinations of outcomes (e.g., presence / absence of any AKI, and/or severe AKI) by logistic regression. Details will be in the SAP.

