### 11.2 Statistical Power and Sample Size Determination

The REFRESH II study hypothesis is that, for patients at increased risk for AKI based upon use of the Cleveland Clinic Score for stratification of the risk of cardiac surgery associated AKI (CSA-AKI), the intra-operative usage of the CytoSorb device in addition to the standard of care in a bypass circuit during cardiopulmonary bypass will decrease the overall incidence and/or proportion of acute kidney injury (AKI) by stage as defined by the Kidney Disease Improving Global Outcomes (KDIGO) clinical practice guideline definition of acute kidney injury. The AKI Stage is scored as 0, 1, 2 or 3. AKI Stage of 0 indicates no AKI, and AKI stages 1, 2 and 3 indicate mild, moderate, and severe AKI, respectively. Success will be defined by demonstrating a shift in distribution toward overall less severe AKI or fewer incidences of AKI in the CytoSorb population.

The distribution of AKI Stage (0, 1, 2, 3) expected in the control group was estimated from prior data. Sample trial outcomes for which power was computed are summarized in **Error! Reference s ource not found.** below for total N=267 patients in the primary analysis subgroup ("without HCA", randomized 1:1). The proportion of "without HCA" patients will be at least 2/3 of the total sample size 400. 420 patients will be enrolled to account for an expected 5% premature withdrawal rate. Power was computed for comparing binomial proportions of patients with AKI Stage 1, 2, or 3 (or i.e., any AKI); proportions with AKI Stage 2 or 3; and for an ordered categorical rank test comparing the distribution of AKI Stages 0, 1, 2, 3 between treatments. Since it is uncertain whether CytoSorb will lower the overall AKI rate or that of Stages 2 and 3, the ordered categorical test will be primary, i.e., the primary null and alternative hypotheses are

- H0:  $\pi 00 = \pi 01$ ,  $\pi 10 = \pi 11$ ,  $\pi 20 = \pi 21$ ,  $\pi 30 = \pi 31$
- H1:  $\{\pi 30 \ge \pi 31 \text{ and/or } (\pi 20 + \pi 30) \ge (\pi 21 + \pi 31) \text{ and/or } (\pi 10 + \pi 20 + \pi 30) \ge (\pi 11 + \pi 21 + \pi 31)\}$  AND one or more of the above is strictly ">"

where  $\pi i0$  is the proportion of control patients in AKI level i (i=0, 1, 2 and 3) and where  $\pi i1$  is the proportion of CytoSorb patients in level i. Note that level i=0 is no AKI. The test of the null

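### The protocol's primary efficacy sub-population omits controls by a drafting slip and leaves out eligible repair-only patients, so the power stated for N=267 is not guaranteed for it

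*Protocol*

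**What the plan says.** Protocol 11.1 builds its efficacy populations in two layers. The parent modified intent-to-treat (mITT) population is "All randomized patients who meet all inclusion criteria through the completion of the surgical procedure". Within it, "The primary sub-population includes all subjects enrolled and randomized to the treatment group who are undergoing valve replacement with another procedure", restricted to surgery without HCA, and 11.1 adds: "This is the primary population for efficacy analyses". The secondary sub-population is aortic reconstruction with HCA, and 11.1 again limits it to the treatment group.

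The primary definition recurs in 6.3.2 ("The intended primary effectiveness sub-population includes all subjects enrolled and randomized to the treatment group who are undergoing valve replacement with another procedure") and in two rows of the synopsis, Study Population and Primary Effectiveness Endpoint. That makes four places in all.

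Eligibility is wider. Inclusion 2a (6.4.1) accepts, without HCA, "Any combination of heart valve replacement or valve repair and another procedure", and excludes only isolated CABG.

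The power section uses a third description. Section 11.2 computes power "for total N=267 patients in the primary analysis subgroup", identifies that subgroup simply as the patients without HCA randomised 1:1, and sets their share at a minimum of two thirds of 400. Table 5 and the group sequential simulations use the same 267.

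The SAP, written after early stopping, lists only the ITT and Safety populations (6.2) and compares arms in ITT only (6.7.1.1). SAP section 5 still refers to protocol 11.2 for the sample size explanation, and SAP 6.9 reports the primary outcome by HCA (Y/N).

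**The concern.** The definition of the primary efficacy population should say who is in it and agree with the sample size calculation. This one does neither, for two separate reasons.

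- **Arms.** A population made up only of treatment-group subjects has nobody to compare them with.
- **Procedure.** A patient having valve repair with another procedure, with no replacement and no HCA, is eligible and is randomised in the without-HCA stratum. That patient is then outside the primary sub-population (no replacement) and outside the secondary one (no aortic reconstruction with HCA). A patient having both repair and replacement fits the primary wording and is not affected.

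At stake is whether the power stated for N=267 applies to the population that 11.1 calls primary. The intended scope cannot be settled from the text. Section 4 singles out valve replacement on the strength of the earlier trial and describes the primary subgroup in those terms, whereas 11.2 counts the whole without-HCA group.

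**Working it through.** **Inputs**
- N: 400 × 2/3 = 266.7, rounded to 267, 1:1, about 133.5 per arm (11.2).
- Stages 0/1/2/3 (Table 5): control 24/47/26/3%; CytoSorb 36/53/10/1% (Example 1) and 44/40/14/2% (Example 2).
- One-sided alpha 0.025, Wilcoxon rank sum (11.2). Like Table 5, this check ignores the interim looks.
- Repair-only share r: not in the documents, so assumed to be 10%, 20% or 30% of without-HCA patients.

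**Step 1: reproduce the stated power.** With a pooled-variance normal approximation at 133.5 per arm, the binary outcomes give:
- any AKI: 0.572 (stated 0.57) and 0.936 (stated 0.94);
- stages 2–3: 0.961 (stated 0.96) and 0.723 (stated 0.72).

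For the ordinal outcome, let P = Pr(control stage worse) + ½ Pr(tie).
- Example 1: P = 0.4303 + ½ × 0.3618 = 0.6112.
- Example 2: P = 0.4546 + ½ × 0.3306 = 0.6199.

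Tie-corrected power = Φ{√[3N / (1 − Σp̄³)] × (P − 0.5) − 1.96}, where p̄ is the average of the two arms' proportions in each stage.
- Example 1: 1 − Σp̄³ = 0.842. √(801/0.842) × 0.1112 − 1.96 = 1.47, power 0.93.
- Example 2: 1 − Σp̄³ = 0.870. √(801/0.870) × 0.1199 − 1.96 = 1.68, power 0.95.

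A simulation of the tied rank test (133 v 134, 40,000 replicates) gives 0.935 and 0.96. These agree with the protocol's figure of over 90%. The stated figures therefore rest on both arms and on the full 267.

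**Step 2: keep both arms, restrict to replacement.** N = 267 × (1 − r), with the effect unchanged.

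| r | N | Example 1 | Example 2 |
|---|---|---|---|
| 0 | 267 | 0.93 | 0.95 |
| 10% | 240 | 0.90 | 0.93 |
| 20% | 214 | 0.87 | 0.90 |
| 30% | 187 | 0.82 | 0.86 |

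Simulation agrees to about one point.

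**Step 3: can 267 replacement patients still be reached?** Without-HCA patients needed = 267 / (1 − r).
- 10%: 297 (74% of 400).
- 20%: 334 (83.5%).
- 30%: 382 (95.5%).
- 40%: 445, more than the 400 planned.

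Up to 30%, this is compatible with a minimum of two thirds, but the plan does not require it.

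**Step 4: effect of including repair-only patients.** Suppose they have a fraction f of the replacement effect. Inclusion keeps N=267 but dilutes the effect to (1 − r) + r·f of its size. It matches exclusion when (1 − r) + r·f = √(1 − r), ignoring the small change in the tie term.
- r = 20%: f = (0.894 − 0.8)/0.2 = 0.47, about half.
- r = 20% and f = 0: P − 0.5 becomes 0.8 × 0.1112 = 0.0890 and 0.8 × 0.1199 = 0.0959. Power is 0.78 (Example 1) and 0.83 (Example 2), against 0.87 and 0.90 with these patients excluded.

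**The case against.** **The missing controls change nothing in practice.** This stands. The parent mITT population covers all randomised patients, 11.1 analyses subjects as randomised, and 11.1.2 sets the criterion "If a significant beneficial effect is met for CytoSorb over control at a one-sided overall 0.025 level of significance". A reader might infer that a one-arm primary analysis was planned. The documents do not support that, and N and power need no change on this account.

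**267 can still be reached.** A reader might infer that the defined population could never reach 267 out of 400 unless nobody had repair alone, so that the stated power is lost. This does not follow, because 11.2 sets two thirds as a minimum. Step 3 shows that 267 replacement patients fit within 400 at shares of 10% to 30%. What remains is that nothing in the plan secures them.

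**The matter is superseded.** Enrolment ended at 151 including roll-ins, before any interim analysis (SAP 4.1), and no mITT sub-population is analysed in the SAP. This stands for the reported comparison. Section 6.3.2 did treat the definition as provisional, to be confirmed at the interim analysis, but that step never took place.

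**Adding repair-only patients is more than rewording.** This stands in part. Section 4 gives a reason for preferring replacement, and Step 4 shows that inclusion can cost power. The choice belongs to the sponsor.

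**Conclusion.** The primary sub-population is wrong as written and does not match the group that was powered. The omission of controls is a drafting error. The repair-only gap is a real inconsistency between 11.1, 6.4.1 and 11.2, and the documents do not say which population was meant.

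If exactly 267 patients are without HCA and the effect is as in Table 5, a repair-only share of 10% to 30% brings ordinal power to between 0.90 and 0.82 (Example 1) or between 0.93 and 0.86 (Example 2). Example 1 is clearly under the stated 90% by a 20% share, and both examples stay above 0.80 at 30%. The share is an assumption throughout.

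A reader might also infer that the trial's reported primary result is compromised. It is not, because the SAP compares arms in ITT, which includes both arms and the repair-only patients.

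**What to change.** 1. In all four places (both synopsis rows, 6.3.2 and 11.1), replace the restriction to the treatment group with randomisation to either arm. Do the same for the secondary sub-population in 11.1.
2. Make 11.1 agree with 6.4.1 and 11.2. The definition that matches N=267 and the stratification in 8.5.1 is all subjects, in both arms, in the stratum with no intended HCA, whether replacement or repair. The secondary sub-population is then the intended-HCA stratum. If replacement only was meant, say so, state where repair-only patients belong, and restate N and power for that group.
3. In SAP 6.9, state that HCA (Y/N) is classified by intended use at randomisation. That is the stratification factor, and protocol 8.4 recognises that the procedure may change on the day of surgery.

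Items 1 and 3 cost only wording. Item 2 is a decision about the population: including repair-only patients keeps the stated N but lowers power, compared with leaving them out, if their effect is less than about half that of replacement patients.
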